### 17.3.1. ECG SPECIFIC DERIVATIONS

[figure not shown]
- $QTcF (msec) = \frac{QT (ms)}{\sqrt[3]{RR (ms)/1000}}$
- $QTcB (msec) = \frac{QT (ms)}{\sqrt{RR (ms)/1000}}$

### 17.3.2. ECG MARKEDLY ABNORMAL CRITERIA

Markedly abnormal quantitative ECG measurements will be identified in accordance with the following predefined markedly abnormal criteria ([Guidance for industry: E14: clinical evaluation of QT/QTc interval prolongation and proarrhythmic potential for non-antiarrhythmic drugs.](#)):

- Observed values for QT interval, QTcB and QTcF will be classified as:
  - >450 msec with no pre-existing condition i.e., Baseline ≤450 msec
  - >480 msec with no pre-existing condition i.e., Baseline ≤450 msec
  - >500 msec with no pre-existing condition i.e., Baseline ≤450 msec
- Change from Baseline for QT interval and QTcF will be classified as:
  - >30 msec increase from Baseline
  - >60 msec increase from Baseline

## 17.4. VITAL SIGNS

The following vital signs measurements will be reported for this study based on SAF.

- Seated and standing systolic blood pressure (SBP) (mmHg)
- Seated and standing diastolic blood pressure (DBP) (mmHg)
- Seated and standing pulse rate (bpm)
- Respiratory rate (breaths/min)
- Body temperature
- Weight

### 17.4.1. BODY TEMPERATURE, RESPIRATORY RATE, AND WEIGHT

The following summaries will be provided:

- Observed values and change from Baseline to end of period
- Shift from Baseline to end of period when observations are categorized into Low/Normal/High (refer to Table 6)

[figure not shown]
### 17.4.2. SEATED BLOOD PRESSURE AND PULSE RATE

The average of all measurements collected during the Baseline visit and of all measurements collected during the end of period visit post-dose timepoints will be computed and the following summaries will be provided:

- Average observed values and average change from Baseline to the end of period visit;
- Shift from Baseline to end of period visit when average observed values are categorized into Low/Normal/High (refer to Table 6);
- Incidence of subjects with average change from Baseline to end of period visit meeting the following criteria:
  - Decrease/increase in SBP  $\geq 10$ ,  $\geq 20$ , and  $\geq 30$  mmHg
  - Decrease/increase in DBP  $\geq 10$ ,  $\geq 20$ , and  $\geq 30$  mmHg
  - Decrease/increase in pulse rate (HR)  $\geq 15$  and  $\geq 30$  beats per minute

The average of the 2 (or 3, when applicable) measurements collected during each end of period visit pre-dose and post-dose timepoints will also be computed and the following summaries will be provided:

- Average observed values and average changes from the end of period visit pre-dose timepoint to each end of the period visit post-dose timepoint;

- Average observed values and average changes from each baseline visit timepoint to time-matched end of period visit timepoint, where the 0-hour baseline timepoint is matched with the pre-dose end of period visit timepoint, the 2-hour baseline timepoint with the 1-hour post-dose end of period timepoint, the 3-hour baseline timepoint with the 2-hour post-dose end of period visit timepoint, and the 5-hour baseline timepoint with the 4-hour post-dose end of period timepoint;
- Shift from end of period visit pre-dose timepoint to each end of period post-dose timepoint when average observed values are categorized into Low/Normal/High (refer to Table 6);
- Shift from each baseline visit timepoint to time-matched end of period visit timepoint when average observed values are categorized into Low/Normal/High;
- Incidence of subjects with average change from end of period pre-dose timepoint to each end of period visit post-dose timepoint meeting the criteria described above;
- Incidence of subjects with average change from each Baseline timepoint to time-matched end of period visit timepoints meeting the criteria described above

The following listings will be provided:

- Listing of subjects with any abnormal average observed values for averages computed over the Baseline visit and end of period visit post-dose timepoints (low/ high);
- Listing of subjects with any abnormal average observed values for averages computed over each visit timepoint (low/ high);

The following figures will be provided:

- Lines plots of mean average time-matched observed values across visit by treatment group;

[figure not shown]
### **17.4.3. ORTHOSTATIC HYPOTENSION**

For each timepoint where 2 or 3 seated measurements will be collected, the average of these measurements will be computed and used in the following analyses:

- Summary of observed values and change from seated to standing (1 minute and 3 minutes, separately) position in observed values by timepoint and visit as well as changes from Baseline to time-matched end of period visit in change from seated to standing position
- Listing of subjects who meet the criteria for orthostatic hypotension (having a decrease in SBP  $\geq 20$  mmHg or decrease in DBP  $\geq 10$  mmHg) at any timepoint
- For the subset of subjects who meet the criteria for orthostatic hypotension: average observed values and average changes from each baseline visit timepoint to time-matched end of period visit timepoint

### **17.4.4. VITAL SIGNS REFERENCE RANGES AND MARKEDLY ABNORMAL CRITERIA**

Vital Signs average observed values will be compared with the relevant reference ranges (refer to Table 6) and categorized as:

- Low: result < LLN
- Normal: result within the laboratory normal reference range (upper and lower limit included)
- High: result > ULN

**Table 6 Vital Signs Reference Ranges**

Variable (unit)	Low	High
SBP (mmHg)	≤ 90 mmHg	≥ 155 mmHg
DBP (mmHg)	≤ 60 mmHg	≥ 95 mmHg
Pulse rate (bpm)	F: ≤ 55 bpm ; M: ≤ 50 bpm	F: ≥ 95 bpm ; M: ≥ 90 bpm
Respiratory rate (breaths/min)	<12	>30

Note: bpm: Beats per minute. DBP: Diastolic Blood Pressure. F: Female. HR: Heart Rate. M: Male. mmHg: Millimeter of mercury. SBP: Systolic Blood Pressure.

## 17.5. COLUMBIA-SUICIDE SEVERITY RATING SCALE

[figure not shown]
The Columbia-Suicide Severity Rating Scale (C-SSRS) is a widely used measure of suicidal ideation and behavior. The instrument reliably predicts a potential suicide attempt in those who had previously attempted suicide and is able to determine clinically meaningful points at which a person may be at risk for an impending suicide attempt (Posner *et al* 2011).

The Screening/Baseline version of the C-SSRS will be administered to subjects at the Screening Visit. Suicidal ideation will be assessed for lifetime and over the past 12 months, and suicidal behavior will be assessed for lifetime and over the past 5 years with the Baseline/Screening Version of the C-SSRS.

The Since Last Visit Version of the C-SSRS will be administered to subjects at the Baseline visit; Visits 3, 4, 5, and 6/Early Termination; and at the Safety Follow-up visit.

The following summaries will be provided for the C-SSRS data from the Since Last Visit Version across all periods based on SAF:

- Number and percentage of subjects with any suicidal behavior (i.e., having responded yes to any of the 4 types of suicidal behavior) or any suicidal ideation (i.e., having responded yes to any of the 5 types of suicide ideation); a subject having reported both suicidal behavior and suicidal ideation will be counted only once
- Number and percentage of subjects with any suicidal behavior as well as broken down by type of suicidal behavior
- Number and percentage of subject with any emergent suicidal behavior (i.e., no suicidal behavior at Baseline and having responded yes to any of the 4 types of suicidal behavior during treatment) compared to:

- Lifetime
- Past 5 years
- Number and percentage of subjects with any suicidal ideation as well as broken down by type of suicidal ideation
- Number and percentage of subject with any emergent suicidal ideation (i.e., no suicidal ideation at Baseline and having responded yes to any of the 5 types of suicidal ideation during treatment) compared to:
  - Lifetime
  - Previous 12 months
- Number and percentage of subjects with any emergent serious suicidal ideation (i.e., no suicidal ideation at Baseline and having responded yes to at least one of the 2 following types of suicidal ideation during treatment: 'active suicidal ideation with some intent to act, without specific plan' and 'active suicidal ideation with specific plan and intent') compared to:
  - Lifetime
  - Previous 12 months

All C-SSRS parameters will be presented in the subject data listing.

## 18. PHARMACOKINETIC DATA

### 18.1. GENERAL CONSIDERATIONS

[figure not shown]
Subjects who enrolled in the study prior to Amendment 2 implementation would have participated in the PK evaluation. Blood samples for PK analysis were collected from each of these subjects at pre-dose and at 1, 2, 3, 4, 5, and 6 hours after dosing at Visits 3, 4, 5, and 6. A sample was also collected 7 to 8 hours after dosing, as feasible, at each study center visit.

Some minor modifications may be necessary to the planned design of tables, figures, and listings to accommodate data collected during the actual study conduct.

Quantitative variables will be summarized using descriptive statistics, including N, arithmetic mean, SD, coefficient of variation (CV%), median, minimum, maximum, geometric mean, geometric SD and geometric CV (GCV%) values. Geometric statistics will be included for PK concentrations and parameters, where applicable.

All PK concentrations will be reported and analyzed with the same precision as the source data provided by the bio-analytical laboratory regardless of how many significant figures or decimals the data carry. Derived PK parameters will be rounded for reporting purposes in by-subject listings. The rounded derived PK data will be considered the source data for the calculation of descriptive statistics and the statistical analysis. For most derived PK parameters, 3 significant digits will be used as the standard rounding procedure, with the following exceptions:

- Parameters directly derived from source data (e.g., maximum concentration [ $C_{max,ss}$ ]) will be reported and analyzed with the same precision as the source data.

- Parameters derived from actual elapsed sample collection times (eg, time to maximum concentration [ $t_{max,ss}$ ]) will be reported with the same precision as the actual elapsed sampling time value of the source data.

For the reporting of descriptive statistics, the arithmetic and geometric means and SDs, will be presented to one digit more precision than the source data. The minimum, median, and maximum will be presented to the same precision as the source data. The CV% and GCV% will always be reported to 1 decimal place.

## 18.2. CONCENTRATION DATA

Subjects with partial concentration data will be evaluated on a case-by-case basis to determine if sufficient data are available for reliable estimation of PK parameters.

A listing of PK blood sample collection times as well as derived sampling time deviations will be provided.

Plasma concentrations will be summarized using descriptive statistics for each treatment. Concentrations that are below the limit of quantitation (BLQ) will be treated as a numeric value of zero and the associated geometric statistics designated as not done.

A subject listing of all concentration-time data for each treatment will be presented. Figures of arithmetic mean concentration-time data ( $\pm$ SD, as appropriate) will be presented on linear and semi-logarithmic scales with all active treatments displayed in the same graph.

[figure not shown]
Individual by subject concentration-time data and spaghetti plots will be generated and presented by treatment on linear and semi-logarithmic scales.

## 18.3. PHARMACOKINETIC PARAMETERS

For PK parameter calculations, pre-dose samples that are BLQ or missing will be assigned a numerical value of zero. Any other BLQ concentrations will be assigned a value of zero if they precede quantifiable samples in the initial portion of the profile. A BLQ value that occurs between quantifiable data points, especially prior to  $C_{max}$ , will be evaluated to determine if an assigned concentration of zero makes sense, or if exclusion of the data (flagged out and treated as missing) is warranted. Following  $C_{max}$ , BLQ values embedded between 2 quantifiable data points will be treated as missing when calculating PK parameters. If a BLQ value occurs at the end of the collection interval (after the last quantifiable concentration), it will be set to zero. If consecutive BLQ concentrations are followed by quantifiable concentrations in the terminal portion of the concentration curve, these quantified values will be excluded from the PK analysis by setting them to missing, unless otherwise warranted by the concentration-time profile. Actual elapsed time from dosing on active treatment visits will be used for PK parameter calculations.

Plasma PK parameters to be calculated for JZP-110 concentrations by non-compartmental methods will include, but may not be limited to the following, as appropriate:

AUC 0-t,ss	Area under the plasma concentration-time curve from time zero (pre-dose) to time of last quantifiable concentration at time t, calculated by the Linear trapezoidal / Linear Interpolation summation method.
-----------------------	--

$C_{max,ss}$	Maximum plasma concentration, obtained directly from the observed concentration versus time data.
$t_{max,ss}$	Time of maximum plasma concentration, obtained directly from the observed concentration versus time data.
$t_{1/2}$	Apparent terminal elimination half-life, determined as $\ln(2)/K_{el}$ .
$K_{el}$	Apparent terminal elimination rate constant estimated by unweighted log-linear regression of the last portion of the plasma concentration profile.
$AUC_{0-tau}$	Area under the plasma concentration-time curve from time zero (pre-dose) through the dosing interval. Given the 24 hour dosing interval and blood collections for PK available through 8 hours, the estimated value will reflect an extrapolation and should be considered with caution.
$CL/F_{ss}$	Apparent oral systemic clearance, calculated as $Dose/AUC_{0-tau}$ .
$Vd/F_{ss}$	Apparent oral volume of distribution, calculated as $Dose/K_{el} \times AUC_{0-tau}$ .

In addition, dose normalized  $AUC_{0-t,ss}$  and  $C_{max,ss}$  may be reported.

The following PK parameters will be calculated for diagnostic purposes and listed, but will not be summarized.

[figure not shown]
$t_{1/2}$ , Interval	The time interval (h) of the log-linear regression to determine $K_{el}$ .
$t_{1/2}$ , N	Number of data points included in the least squares log-linear regression analysis to determine $K_{el}$ . A minimum of the last 3 quantifiable data points excluding $t_{max,ss}$ will be used for determination.
Rsq	Goodness-of-fit statistic for calculation of $K_{el}$ (Regression coefficient).

Pharmacokinetic parameters will be summarized by treatment using descriptive statistics. Geometric mean will not be calculated for  $t_{max}$ . A subject listing of individual PK parameters for each treatment will be provided. For  $t_{max}$  a frequency table will also be provided.

Scatter plots of individual and mean PK parameters versus treatment will be presented. Additionally, graphical presentations of PK data may be added at the discretion of the PK scientists, if further illustration of the PK results is deemed appropriate.

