### 1.3.1 Clinical Pharmacokinetics and Product Metabolism

JZP-110 is eliminated primarily via the renal route, with at least 90% of the dose being excreted as unchanged drug within 48 hours. Following single dosing and repeated doses administered twice daily, JZP-110 exposure was dose-proportional, absorption (time to maximum plasma concentration [ $t_{max}$ ]: 1.3 to 3.0 hours) and elimination ( $t_{1/2}$ : 5 to 7.6 hours) were relatively rapid, and steady state was reached in 3 days. JZP-110 displayed linear PK during 14 days of dosing over the dose range of 200 to 1000 mg per day. Limited accumulation and no enzyme auto-induction were evident.

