### 6.13.2 Pharmacokinetic Parameters

Plasma PK parameters to be calculated for JZP-110 concentrations will include, but may not be limited to, the following, as appropriate:

AUC 0-t	Area under the plasma concentration versus time curve from time 0 to t hours, the last detectable concentration, calculated by means of the trapezoidal rule
AUC 0-inf	Area under the plasma concentration versus time curve from time 0 to infinity, calculated as $AUC = AUC_{0-t} + C_t / K_{el}$ , where $C_t$ is concentration at time t, and $K_{el}$ is the elimination rate constant estimated from the fitted terminal elimination phase (see $K_{el}$ )
$C_{max}$	Maximum plasma drug concentration
$T_{max}$	Time to reach $C_{max}$
$t_{1/2}$	Apparent terminal elimination half-life, calculated as $\ln(2) / K_{el}$
$K_{el}$	Apparent elimination rate constant estimated by unweighted log-linear regression of the last portion of the plasma concentration profile. This log-linear regression will be fitted according to the least-squares approach. Starting with the last 3 quantifiable measurements and stepping back, the best fit will be determined by minimizing the residual sums of squares; the time interval and the number of time points used for this optimal fit will be provided.
CL/F	Apparent oral clearance (calculated as Dose/AUC inf )
Vd/F	Apparent oral volume of distribution (calculated as oral clearance/ $K_{el}$ )

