### **3.5. SCHEDULE OF EVENTS**

Refer to Table 2 and Table 3 for the schedule of events for Group 1 and Group 2, respectively.

In addition, subjects who enrolled in the study prior to Amendment 2 implementation would have participated in the PK evaluation. Blood samples for PK analysis were to be collected from each subject at pre-dose and at 1, 2, 3, 4, 5, and 6 hours after dosing at Visits 3, 4, 5, and 6. A sample was also collected any time between 7 to 8 hours after dosing, if feasible, at each center visit.

[figure not shown]

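### AUC0-t,ss has no common end time: it stops near 6 h or at 7 to 8 h depending on an optional sample, so its summary by dose mixes time windows

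*SAP*

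**What the plan says.** SAP 18.3 defines AUC0-t,ss as "Area under the plasma concentration-time curve from time zero (pre-dose) to time of last quantifiable concentration at time t", by the linear trapezoidal rule. Protocol 6.13.2 leaves the end equally open: "the last detectable concentration, calculated by means of the trapezoidal rule". On timing, SAP 18.3 adds: "Actual elapsed time from dosing on active treatment visits will be used for PK parameter calculations".

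SAP 18.1 puts the PK samples at "pre-dose and at 1, 2, 3, 4, 5, and 6 hours after dosing at Visits 3, 4, 5, and 6". Of the late sample it says: "A sample was also collected 7 to 8 hours after dosing, as feasible, at each study center visit". SAP 3.5 makes the band explicit: "A sample was also collected any time between 7 to 8 hours after dosing, if feasible, at each center visit".

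SAP 18.3 then summarises the PK parameters by treatment with descriptive statistics and plots individual and mean values against treatment. A sentence opening "In addition, dose normalized" allows dose-normalised AUC0-t,ss and Cmax,ss to be reported. Neither document sets a common upper limit, defines a partial area such as AUC0-6h, or splits the summary by end time.

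**The concern.** An area to the last quantifiable concentration works well when sampling follows the curve until drug has almost gone. The end time then matters little, because the remaining area is small. Here sampling stops 6 to 8 h after dosing, against a half-life of 5 to 7.6 h. The end time is then set by whether and when the subject gave the last sample, and the piece of area at issue is not small.

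Two visits with identical exposure can therefore give different AUC0-t,ss values. AUC0-t,ss is also the only AUC in SAP 18.3 not flagged as extrapolated: the SAP says AUC0-tau rests on extrapolation and should be read with caution. A reader comparing exposure across 75, 150 and 300 mg is likely to turn to AUC0-t,ss first.

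**Working it through.** The documents give no numerical AUC, so there is no figure to reproduce. The check asks which sample sets the end time, then sizes the effect.

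**Inputs.** Half-life 5 to 7.6 h and tmax 1.3 to 3.0 h (Protocol 1.3.1). Scheduled samples at 0, 1, 2, 3, 4, 5 and 6 h, with an optional one at 7 to 8 h (SAP 18.1 and 3.5). Linear trapezoids (SAP 18.3). Dosing every 24 h. The one-compartment oral model is an assumption. The share of visits with a late sample is not given, so it is varied.

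**Model.** At steady state, per unit dose/volume,

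C(t) = ka/(ka − ke) × [e^(−ke·t)/(1 − e^(−24ke)) − e^(−ka·t)/(1 − e^(−24ka))],

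with ke = ln 2 / half-life and ka solved to give the chosen tmax. The grid was half-life 5, 6 and 7.6 h by tmax 1.3, 2 and 3 h.

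**Step 1: which sample sets t.** Over the grid, C(6 h) is 56–85% of Cmax and C(8 h) is 42–72%. On active doses the last sample taken should normally be quantifiable. So t is about 6 h without the late draw and 7 to 8 h with it.

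**Step 2: one case in full (half-life 6 h, tmax 2 h).** ke = 0.693/6 = 0.1155 and ka = 1.29. Concentrations at 0 to 6 h are 0.0732, 0.7414, 0.8467, 0.8055, 0.7317, 0.6558 and 0.5853. At 7, 7.5 and 8 h they are 0.5218, 0.4925 and 0.4649.

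- AUC0-6 = 0.0732/2 + (0.7414 + 0.8467 + 0.8055 + 0.7317 + 0.6558) + 0.5853/2 = 4.110
- Last sample at 7 h: 4.110 + (0.5853 + 0.5218)/2 = 4.664; ratio 1.135
- Last sample at 7.5 h: 4.110 + 0.75 × (0.5853 + 0.4925) = 4.919; ratio 1.197
- Last sample at 8 h: 4.110 + (0.5853 + 0.4649) = 5.161; ratio 1.256

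**Step 3: the full grid.**

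| Last sample | AUC0-t / AUC0-6h |
|---|---|
| 7 h | 1.117–1.160 |
| 7.5 h | 1.170–1.236 |
| 8 h | 1.220–1.308 |

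Even when the late sample exists, drawing it at 8 h rather than 7 h changes the area by 9–13%.

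**Step 4: effect on a summary by dose (late draw at 7.5 h).** Let r be the ratio in Step 3, so r = 1.170 to 1.236.

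- Spread within a dose, half the visits having the late sample: CV from the window alone = (r − 1)/(r + 1), which is 0.170/2.170 = 0.078 to 0.236/2.236 = 0.106.
- Ratio of dose-normalised means at two doses with late-sample shares p1 and p2 and truly proportional exposure: [1 + p1(r − 1)]/[1 + p2(r − 1)].

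| Shares at the two doses | Spurious ratio |
|---|---|
| equal | 1.00 |
| 90% v 50% | 1.153/1.085 = 1.06 to 1.212/1.118 = 1.08 |
| 75% v 25% | 1.128/1.043 = 1.08 to 1.177/1.059 = 1.11 |
| 100% v 0% | 1.17 to 1.24 |

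With a fixed 0–6 h window, the ratio for an identical profile with and without the late sample is 1.00.

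**The case against.** **Bias between doses is not shown.** It needs the share or timing of late samples to differ by dose. The schedule is the same at Visits 3 to 6, and the documents give no shares. This stands. The most that can be said is that the design offers a route: active dose always rises with visit number (Visits 4, 5, 6 in Sequence A; 3, 4, 5 in Sequence B), so a drift over visits in staying for the last draw would look like a drift by dose.

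**The added spread is modest next to ordinary variability.** If between-subject CV were 20% (an assumption), an independent window CV of 7.8–10.6% would raise it to √(0.20² + 0.078²) = 21.5% up to √(0.20² + 0.106²) = 22.6%. From 40% it would rise to about 41%. This stands too.

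**Other provisions help.** SAP 18.2 reviews partial profiles case by case, lists sample times and plots individual curves. The parameter list is open-ended, and AUC0-tau has a nominal common window. These let a reader recover t, but they do not standardise the summarised area. A complete 0–6 h profile could pass the review and still have a different window from its neighbours.

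**Some detail is out of view.** Protocol 6.10.2.2 and 6.13.1 refer to Protocol Amendment 1 for blood collection. A rule for the late draw may be there, but the SAP text still makes the sample optional.

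**Stronger readings to avoid.** A reader might infer that the plan will distort a dose-proportionality result, or that AUC0-t by dose will be wrong by 10–24%. Neither follows. No proportionality test is planned, and dose-normalisation is optional. The 10–24% (1 − 1/1.117 to 1 − 1/1.308) describes one subject who gives the late sample at one dose and misses it at another; it is not the error in a treatment mean.

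**Conclusion.** The structural point holds on the wording of the SAP alone: if the optional sample is sometimes missed or its time varies, AUC0-t,ss summarised by treatment mixes windows of about 6 h and 7 to 8 h. For an identical profile the difference is 12–31%, depending on when the last sample falls. That range rests on the one-compartment steady-state model with the protocol's half-life and tmax.

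Extra spread within a dose follows whenever t varies. Bias between doses is conditional on an imbalance that the documents neither report nor exclude.

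The reach is narrow. Cmax and tmax do not depend on t, and CL/F and Vd/F use AUC0-tau. PK is a descriptive secondary objective in subjects enrolled before Amendment 2. This is a cheap improvement worth making. It does not threaten the trial's conclusions.

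**What to change.** In SAP 18.3, add AUC0-6h,ss: a partial area by linear trapezoid over the interval scheduled at every PK visit, with actual times interpolated to 6.0 h. State the rule for the awkward case: if the nominal 6 h sample is slightly early and no later sample exists, take the area to that sample's actual time. In the worked case, stopping at 5.9 h loses about 0.1 × 0.585/4.110 = 1.4%.

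Use AUC0-6h,ss for comparison by treatment, for plots against treatment and for dose-normalisation. Keep AUC0-t,ss, which the protocol defines, and report it with its t. There is no need to move it to listings only. Record the addition in SAP 3.6.

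The cost is one extra parameter, a few lines of SAP text and a partial-area setting in the noncompartmental software, with no new samples. The drawback is that the 6 to 8 h segment is left out of the comparison area. It remains in AUC0-t,ss, the listings and the concentration plots.

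### AUC0-tau is extrapolated from 6–8 h to 24 h by an unstated method, while the steady-state pre-dose sample that estimates the 24 h concentration goes unused and is set to zero when missing

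*SAP*

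**What the plan says.** SAP 18.1 describes PK blood collection "at pre-dose and at 1, 2, 3, 4, 5, and 6 hours after dosing at Visits 3, 4, 5, and 6". The later sample was optional: "A sample was also collected 7 to 8 hours after dosing, as feasible, at each study center visit". A profile therefore ends at 7–8 h, or at 6 h where the last sample was not feasible.

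SAP 18.3 lists AUC0-tau among the parameters and is open about its weakness. It sets the 24 h interval against sampling that stops at 8 h and warns that "the estimated value will reflect an extrapolation and should be considered with caution". It does not state how the extrapolation is done. Clearance depends directly on it ("Apparent oral systemic clearance, calculated as" dose over AUC0-tau). Vd/F depends on both AUC0-tau and Kel, and its formula is printed without parentheses. Kel is a log-linear fit to the last part of the profile, with this lower limit on points: "A minimum of the last 3 quantifiable data points excluding" the time of the maximum.

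For parameter calculation, "pre-dose samples that are BLQ or missing will be assigned a numerical value of zero".

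Protocol 1.3.1 gives a half-life of 5 to 7.6 h and a time to maximum of 1.3 to 3.0 h, and says that "steady state was reached in 3 days". Under SAP 3.1, each PK visit closes a week of once-daily dosing at one level.

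**The concern.** At steady state with once-daily dosing, the concentration just before a dose equals the concentration 24 h after it. The pre-dose sample at Visits 3 to 6 is such a trough. The plan therefore holds a measured value near the far end of the interval but leaves two thirds of that interval (16 of 24 h) to an extrapolation it does not specify.

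At stake is the precision of individual AUC0-tau, CL/F and Vd/F. Characterising PK in Parkinson's disease is a secondary objective, and the PK population is limited to subjects enrolled under the original protocol or Amendment 1. Extrapolation noise would appear in the summaries as extra between-subject variability in clearance.

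Setting a missing pre-dose value to zero fits a first dose, when no drug is yet present. It does not fit a trough after a week of dosing.

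**Working it through.** The documents give no extrapolated share or precision to reproduce, so the check is built from their PK figures.

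**Inputs**
- Interval 24 h; last sample at 7.5 h (within 7–8 h) or 6 h: SAP 18.1 and 18.3.
- Half-life 5 and 7.6 h, so ke = ln 2 / half-life = 0.1386 and 0.0912 per h: Protocol 1.3.1.
- Absorption rate ka = 1.2 per h (assumption). It implies a single-dose tmax of ln(ka/ke)/(ka − ke) = 2.0 and 2.3 h, inside the protocol's 1.3–3.0 h.
- Residual CV 5, 10 and 15%, log-normal (assumption; no document gives a figure).
- One-compartment oral model (assumption).

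**1. Is the pre-dose sample a steady-state trough?** The fraction of steady state after 72 h is 1 − 0.5^(72/half-life): 99.99% at 5 h and 99.86% at 7.6 h. This agrees with the protocol's statement. After six days it exceeds 99.999%.

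**2. Share of AUC0-tau beyond the last sample.** In scaled units, C(t) = e^(−ke·t)/(1 − e^(−24ke)) − e^(−ka·t)/(1 − e^(−24ka)), and AUC0-tau = 1/ke − 1/ka.
- Half-life 5 h: AUC0-tau = 7.213 − 0.833 = 6.380. Beyond 7.5 h: 2.377/6.380 = 37%. Beyond 6 h: 2.988/6.380 = 47%.
- Half-life 7.6 h: AUC0-tau = 10.964 − 0.833 = 10.131. Beyond 7.5 h: 4.847/10.131 = 48%. Beyond 6 h: 5.760/10.131 = 57%.

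Varying tmax over 1.3–3.0 h gives 32–47% with a last sample at 8 h and 44–59% at 6 h.

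**3. Cost of the zero rule.** The true trough is 5–16% of Cmax. Setting it to zero removes 0.5 h × C(0) from the first trapezoid.
- Smallest: half-life 5 h, C(0) = 0.0372, AUC0-7.5 = 6.380 − 2.377 = 4.003; loss 0.0186/4.003 = 0.5%.
- Largest: half-life 7.6 h, C(0) = 0.126, AUC0-6 = 10.131 − 5.760 = 4.371; loss 0.063/4.371 = 1.4%.

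**4. Precision of AUC0-tau and CL/F.** Simulation of 20,000 profiles per setting, with a linear trapezoid to the last sample, then either Kel extrapolation or a log-linear join to the observed pre-dose value at 24 h. Geometric CV, half-life 5 h / 7.6 h:

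| Residual CV, Kel points, last sample | Kel extrapolation | Tied to trough |
|---|---|---|
| 5%, 5 points, 7.5 h | 5% / 7% | 2% / 2% |
| 10%, 5 points, 7.5 h | 10% / 13% | 4% / 4% |
| 10%, 3 points, 7.5 h | 15% / 18% | 4% / 4% |
| 10%, 3 points, 6 h | 22% / 24% | 4% / 5% |
| 15%, 3 points, 6 h | 27% / 28% | 7% / 7% |

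At 10% CV with three points and a last sample at 7.5 h, the 5–95% range of AUC0-tau relative to truth is 0.83–1.36 (5 h) and 0.77–1.39 (7.6 h) by extrapolation, against about 0.93–1.07 by the trough. At 10% CV, Kel from three points is not positive in about 1–10% of profiles.

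**5. Vd/F.** At 10% CV with three points and a last sample at 7.5 h, the geometric CV is 41–67% when AUC0-tau and Vd/F both use the late-sample Kel. It rises to 56–87% if only AUC0-tau is tied to the trough, because errors in Kel and AUC0-tau then no longer partly cancel. It is about 8–11% if Kel also comes from the segment between the last sample and the trough.

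**6. Dependence on the prior dose.** If the previous dose was 26 h rather than 24 h earlier, trough-anchored AUC0-tau shifts by about −4%. If it was skipped, the shift is about −25 to −32%, against about −4 to −11% by extrapolation.

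**The case against.** The strongest reply is that the SAP already handles this. It warns about the parameter, reviews partial profiles case by case, lists the fit interval, number of points and goodness of fit, reports Cmax and AUC0-t without extrapolation, and allows population modelling. That stands as disclosure. None of it supplies the missing method or uses the trough.

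A second objection concerns the trough itself. Home doses are taken within an hour of waking and may be late or skipped (Protocol 3.1), while the example clinic dose is at 9:00 after pre-dose procedures. Gaps longer than 24 h are plausible and bias in one direction, whereas Kel extrapolation is nearly unbiased in the median in most settings. This also stands, and it limits the fix: step 6 gives its size.

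Three stronger readings are tempting but unsupported.
- A reader might infer that the SAP prescribes extrapolation with Kel from three points. It states no formula, and three is a minimum. Protocol 6.13.2 steps back from three points and minimises the residual sum of squares, which never falls when a point is added, so that rule would favour three. The SAP does not repeat it. Five points still leave extrapolation less precise than the trough.
- A reader might infer that the terminal points always span under half a half-life. Samples at 5, 6 and 7.5 h span 2.5 h, exactly half of 5 h; samples at 5, 6 and 8 h span 0.6.
- A reader might infer that tying AUC0-tau to the trough repairs everything derived from it. Vd/F gets worse unless Kel changes too.

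**Conclusion.** The point holds as a low-cost improvement of minor weight. About 37–57% of AUC0-tau is extrapolated by an unstated method, and a sample already collected would reduce the geometric CV of individual AUC0-tau and CL/F from about 5–28% to 2–7%. The shares follow from the protocol's half-life and an absorption rate consistent with its tmax. The precision figures also rest on the assumed 5–15% residual CV, three to five terminal points, a one-compartment model and a prior-dose gap of about 24 h.

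The zero rule is wrong in principle at steady state, but its effect on AUC0-t is only about 0.5–1.4%, so it does not by itself distort the results. It would matter more under the fix, because a log-linear join to zero cannot be computed. PK is summarised descriptively, and no efficacy or safety conclusion depends on it.

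**What to change.** Amend SAP 18.3 as follows.

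- Compute AUC0-tau by log-linear interpolation from the last quantifiable sample to the same visit's observed pre-dose value, placed at the end of the dosing interval. Use the recorded time of the previous dose where available. Derive CL/Fss from this AUC0-tau. The log rule must be stated, because a linear trapezoid from 7.5 to 24 h would overstate AUC0-tau by about 8–16%.
- Where the pre-dose sample is missing or BLQ, or the previous dose was skipped or clearly mistimed, use the extrapolated method and flag the profile. State its formula, and report the extrapolated value for all profiles as a check.
- For Vd/Fss, either take Kel from the segment between the last sample and the trough, or keep the extrapolated Vd/Fss with its caution. Do not mix the trough-based AUC0-tau with a late-sample Kel. Write the formula as Dose/(Kel × AUC0-tau).
- Treat missing pre-dose samples as missing, not zero.

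The cost is SAP wording, a software setting and a check of prior-dose timing; no new samples are needed. The timing check is the uncertain part. The protocol and SAP describe tablet counts and verification at visits but no record of home dosing times, and they refer to Amendment 1, not available here, for PK sampling details. If no times exist, the 24 h assumption should be stated and known skipped doses excluded from the trough method.
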